12.1 Descriptive Statistics

Standard summary statistics will be calculated for all study variables to be reported. Continuous data will be summarized by statistics including means, standard deviation or error, median, minimum, maximum, and n. Categorical variables will be summarized by statistics including frequency counts and percentages.

For ordinal-scaled variables a combination may be applied where appropriate. Both categorical summary statistics (frequency and percentage) may be presented within a category and continuous summary statistics (means and standard deviations) may be presented of the scores in the category.

For categorical and ordinal variables, percentages will be calculated on non-missing data.

12.2 Protocol deviations

The number and type of protocol deviations will be summarized with descriptive statistics.

12.3 P-values

Unless otherwise specified statistical analyses will be performed using a two-sided hypothesis test at the overall 5% level of significance. P-values will be rounded to three decimal places. If a p-value is less than 0.001 it will be reported as < 0.001 .

13 Interim Analyses

An interim report will be created to show descriptive statistics of group outcomes and report safety events. No formal statistical testing will be conducted.

14 Missing Data Analyses

All efforts will be made to complete follow-ups. All endpoints will be analyzed based on available data and the percentage of missing data will be taken into consideration.

15 Poolability of Data

This study is a multicenter clinical trial and all participating sites will be selected based upon the same criteria and trained according to the protocol. This will ensure generalizability of the study results.

**Table X: Primary Effectiveness Endpoint by Site
6-Month Change from Screening in CNC Word Recognition Test (Group 1)**

Site	Mean ± SD (N)	Median (Min, Max)	P-value ¹ (t-test)	P-value ² (ANOVA)
0029	38.0 ± 2.8 (2)	38.0 (36.0, 40.0)	0.033	0.591
1003	42.2 ± 34.9 (5)	59.0 (-15.0, 72.0)	0.054	
1050	44.3 ± 19.7 (3)	52.0 (22.0, 59.0)	0.060	
1065	61.1 ± 23.5 (7)	68.0 (20.0, 84.0)	< 0.001	
1507	36.3 ± 20.2 (6)	30.0 (14.0, 69.0)	0.007	
1523	46.6 ± 13.3 (5)	42.0 (30.0, 63.0)	0.001	
Sites with one subject (0848, 1141, 2180)	45.7 ± 14.3 (3)	49.0 (30.0, 58.0)	0.031	

¹P-value for paired difference based on a two-sided, paired t-test with a type I error rate of 5%.

²P-value for ANOVA based on a one-way analysis of variance with 6-month change in CNC as the dependent variable and site ID as the independent variable. Sites with one subject were pooled together into one site.

**Table X: Primary Effectiveness Endpoint by Site
1-Month Change from Baseline in CNC Word Recognition Test (Group 2)**

Site	Mean ± SD (N)	Median (Min, Max)	P-value ¹ (t-test)	P-value ² (ANOVA)
0029	-4.0 ± 8.4 (9)	-4.0 (-21.0, 10.0)	0.189	0.487
0848	0.2 ± 6.8 (5)	1.0 (-10.0, 8.0)	0.951	
1003	3.0 ± 10.2 (9)	6.0 (-12.0, 18.0)	0.403	
1050	-6.4 ± 5.5 (7)	-6.0 (-18.0, -2.0)	0.021	
1065	0.6 ± 8.4 (9)	4.0 (-13.0, 12.0)	0.848	
1141	-4.0 ± 8.5 (2)	-4.0 (-10.0, 2.0)	0.626	
1507	3.9 ± 19.5 (8)	-1.5 (-14.0, 49.0)	0.591	
1523	-4.3 ± 8.1 (7)	-6.0 (-15.0, 6.0)	0.212	

¹P-value for paired difference based on a two-sided, paired t-test with a type I error rate of 5%.

²P-value for ANOVA based on a one-way analysis of variance with 1-month change in CNC as the dependent variable and site ID as the independent variable.

16 Deviations from the Statistical Analysis Plan

Any deviation from the statistical methods planned, as specified above, will be documented and discussed in the final study report. Any rationale for such deviation will be presented in the final study report.

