7.1 Primary Variables

There are two primary effectiveness endpoints that will be evaluated within two different groups. The newly implanted group and the existing subjects.

The first primary effectiveness endpoint is the mean improvement of CNC word recognition in quiet at the 6 month time point in comparison to the preoperative baseline score with an appropriately fit hearing aid in the implanted ear. The mean will be collected from the group of newly implanted subjects.

The second primary effectiveness endpoint is the mean CNC word recognition in quiet at the 1 month time point with AI MAP as compared to EC MAP. The mean scores will be collected from the existing subject population.

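### The Group 1 site comparison models raw 6-month CNC change on site alone, so it cannot separate a site difference from a difference in preoperative score

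*SAP*

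**What the plan says.** Section 7.1 defines the Group 1 endpoint as the mean CNC improvement at 6 months "in comparison to the preoperative baseline score with an appropriately fit hearing aid in the implanted ear". The primary endpoint table in Section 11.1 shows screening, 6-month and difference values for the same 31 subjects.

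Section 15 then tabulates the 6-month change by site. Its footnote states that the between-site p-value comes from a "one-way analysis of variance with 6-month change in CNC as the dependent variable and site ID as the independent variable". It adds: "Sites with one subject were pooled together into one site". That leaves seven site levels, and the printed p-value is 0.591. Section 12.3 sets the default as a "two-sided hypothesis test at the overall 5% level of significance".

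For Group 2 the footnote specifies the same form, a "one-way analysis of variance with 1-month change in CNC as the dependent variable and site ID as the independent variable". Neither model contains the baseline score, neither table shows baseline by site, and the SAP has no baseline-adjusted site analysis.

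**The concern.** The Group 1 by-site table is the SAP's only between-site test of the Group 1 primary endpoint. The primary paired t-test works within subjects, so it needs no baseline term. The site test is different because it compares subjects who started from different scores.

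Where change depends strongly on the starting score, two problems are possible. If sites differ in mean preoperative score, the test can show a site difference that reflects only who was implanted there. If they do not differ, baseline variation that could be removed stays in the error term, and the test is weaker than it need be. In the second case a non-significant result is easily read as support for pooling when the test had little chance of showing anything else.

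**Working it through.** **Inputs.** Section 11.1, Group 1 (n = 31): SD 15.2 at screening, 17.2 at 6 months, 22.0 for the difference. Section 15, Group 1 site rows, as mean, SD (n): 38.0, 2.8 (2); 42.2, 34.9 (5); 44.3, 19.7 (3); 61.1, 23.5 (7); 36.3, 20.2 (6); 46.6, 13.3 (5); 45.7, 14.3 (3).

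**1. Reproduce the printed ANOVA.**
- Grand mean = 46.3.
- Between-site sum of squares, Σn(mean − 46.3)² = 2369 on 6 df.
- Within-site sum of squares, Σ(n − 1)SD² = 12126 on 24 df; mean square error 505.3, pooled within-site SD √505.3 = 22.5.
- F = (2369/6)/505.3 = 0.78, p = 0.593. Allowing for rounding of the inputs, p lies in 0.590 to 0.593, so the printed 0.591 reproduces.

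**2. How change depends on baseline.**
- Correlation of screening with 6-month score: (15.2² + 17.2² − 22.0²)/(2 × 15.2 × 17.2) = 42.88/522.88 = 0.082.
- Slope of change on baseline: 0.082 × 17.2/15.2 − 1 = −0.907.
- Correlation of change with baseline: −0.907 × 15.2/22.0 = −0.627; squared, 0.393.
- A 10-point gap in mean preoperative score between two sites therefore shifts their contrast in mean change by about 9 points when 6-month scores are the same.
- By chance alone, a site's mean baseline has a standard error between 15.2/√7 = 5.7 points (n = 7) and 15.2/√2 = 10.7 points (n = 2). Multiplied by 0.907, this puts 5.2 to 9.7 points of noise into its mean change.

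**3. Excess variance.**
- Whole group: 22.0² = 484.0 for raw change; 17.2² × (1 − 0.082²) = 293.9 after adjustment. The ratio is 1.65, or 1.65 × 29/30 = 1.59 after charging one degree of freedom.
- Sampling error: with n = 31, a Fisher 95% interval for the 0.393 is about 0.12 to 0.64, which corresponds to 14% to 181% excess variance.
- The test's own error term is the within-site 505.3, and its reduction needs site baselines that are not printed. Assume the slope of −0.907 holds within sites and a share h of baseline variance lies between sites. The adjusted within-site sum of squares is then 12126 − 0.907² × 15.2² × 30 × (1 − h). For h = 0 this is 6422, so the ratio of mean squares is 505.3/(6422/23) = 1.81. For h = 0.4 it is 8704, and the ratio is 1.34. The excess is therefore about 34% to 81% over that range.

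**4. Power if baseline is unrelated to site.** Simulated with 4,000 runs per row, printed site sizes, within-site SD 22.5, 5% level. The between-site SD is an assumption, because the SAP gives none.

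| Between-site SD | ANOVA | ANCOVA |
|---|---|---|
| 5 | 9.2% | 12.7% |
| 8 | 19.5% | 28.4% |
| 10 | 27.1% | 40.4% |
| 12 | 38.9% | 54.0% |
| 15 | 53.3% | 70.0% |

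**5. Rejection rates if baseline does differ by site.** The share of baseline variance between sites is again an assumption. Ranges cover repeated simulations.

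| Share between sites | ANOVA, no adjusted site effect | ANCOVA, no adjusted site effect | ANOVA, site SD 10 | ANCOVA, site SD 10 |
|---|---|---|---|---|
| 0% | 5% | about 5% | 27–30% | 40–44% |
| 20% | 13–14% | about 5% | 39% | 39% |
| 40% | 25–27% | about 5% | 51% | 38% |

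**6. Group 2.** From SDs 22.8, 22.3 and 10.6: r = (22.8² + 22.3² − 10.6²)/(2 × 22.8 × 22.3) = 904.77/1016.88 = 0.89. Baseline then explains about 8% of the variance of change.

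**The case against.** The declared endpoint is improvement, and a one-way ANOVA of change tests whether mean improvement differs between sites. If a site with low preoperative scores improves more, its result on that endpoint really is different. ANCOVA answers another question: whether sites differ for subjects with the same starting score. That stands. The SAP contradicts nothing here, and the raw analysis should stay.

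A reader might infer that site differences in this trial are confounded with baseline mix. The document does not show that. No baseline by site is printed, and with p = 0.591 no site difference was declared. The exposure comes from the model; the imbalance is unknown.

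A reader might also take 65% as the excess error variance of this test. It is a whole-group figure that ignores site, with wide sampling error.

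Nor can both benefits be claimed at once. The power gain belongs to the case without imbalance, and at a 20% share in step 5 it is gone. The rebuilt F is below 1, which gives no support for a large site spread, although seven small sites cannot exclude one. With 2 to 7 subjects per site, power is modest under either model.

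Finally, Section 15 attaches no decision to the p-value, and the site means, ranges and per-site tests are printed beside it. Because results already stand in the SAP, a covariate added now is a change made with the data in view. All of this limits the weight of the point. None of it is a reason to leave out the adjusted analysis.

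**Conclusion.** The point holds as a low-cost improvement to a supportive analysis. Change falls by about 0.91 points for each point of preoperative score, so the Group 1 site test is exposed to any baseline difference between sites, and the SAP gives the reader no means of seeing whether there is one. Adjustment brings either more power (no systematic imbalance) or protection against false site differences (imbalance). Which applies here cannot be told from the document.

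The slope and the 39% rest on 31 subjects and a linear relation. The power figures rest on assumed between-site SDs.

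Two further inferences are not supported. The Group 1 primary result (mean change 46.3, p < 0.001) is not in doubt, because its paired t-test is unaffected. Nor is there ground to say that adjustment would make the site effect significant. If the between-site sum of squares stayed the same and the error fell by a factor of 1.59 to 1.65, p would be about 0.30 to 0.32, but that sum of squares would change too. Group 2 gains little.

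**What to change.** In Section 15, keep the Group 1 raw table and ANOVA, and add an ANCOVA of 6-month CNC change on site plus screening CNC score. Beside the raw results, report:
- the site p-value from the ANCOVA;
- the adjusted site means with 95% CIs;
- the screening score by site.

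State that the adjusted model was added after the results in the SAP's tables were known. Leave the primary paired t-tests as they are. The same addition for Group 2 is optional.

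No new data are needed. The cost is some SAP wording, one error degree of freedom (24 to 23) and the assumption of one linear slope common to all sites. That assumption is strained by screening scores near the floor (median 6.0, minimum 0.0) and should be stated as a limitation.
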